8.3. Patient Withdrawal Criteria

For all patients, it is the intent that patients who discontinue study medication (at any time) for any reason will continue to be followed for all protocol-planned study visits through the completion of the 24-week treatment period, and will have all endpoints (including efficacy) collected accordingly.

The Investigator, Sponsor, or its designee may decide a patient should discontinue treatment at any time and for any reason. In addition, patients will discontinue randomized treatment if they:

- Experience an intolerable adverse event, including but not limited to bone marrow related events characterized by protocol specified hematologic abnormalities, or a \geq Grade 3 cardiac event, or a \geq Grade 4 (other) adverse event (CTCAE v5.0 criteria) considered possibly related to study drug. Because laboratory abnormalities can occasionally occur that do not in themselves pose an unacceptable risk to subject safety (e.g., CK elevations with exercise, laboratory errors or artifacts), the occurrence of a \geq Grade 4 laboratory abnormality, or any laboratory abnormality of concern to the Investigator, will be discussed with the Medical Monitor and a determination will be made, based on a reassessment of risk-benefit for the subject, whether the subject should discontinue randomized treatment. Documentation on the determination will be maintained in the study files;
- Require a medication that is prohibited by the protocol. However, under certain circumstances, and in consultation with the Medical Monitor, short-term use of a prohibited medication may not necessitate withdrawal of treatment when its use is unlikely to unfavorably alter the risk-benefit of subject participation;
- In the opinion of the Investigator, have any medically appropriate reason;
- Become pregnant;
- Have a serious adverse event associated with a SARS-CoV-2 infection;

- The Investigator believes that further treatment is undesirable or the risk-benefit profile has become unfavorable.

Furthermore, dose interruptions lasting more than 21 days may require treatment discontinuation on a case by case basis following consultation with the Medical Monitor.

In addition, patients are free to withdraw from participation in the study at any time, for any reason, and without prejudice. The Investigator must withdraw any patient from the study if the patient withdraws consent and requests to stop participating in the study. Patients who withdraw or are withdrawn from the study will not be replaced.

8.3.1. Patient Withdrawal Procedures

If a patient withdraws consent from further participation in the study, the Investigator will record the reason(s) for early termination on the relevant electronic case report form (eCRF). The specific reason for the withdrawal should be carefully documented on the eCRF.

8.4. Emergency Unblinding of Treatment Assignment

In the case of a medical requirement to break the blind to determine appropriate treatment for an adverse event, unblinding of a patient's treatment assignment can be achieved through the study-specific Interactive Web Response System. If possible, the Investigator should discuss the circumstances with the Medical Monitor(s) prior to accessing unblinding information. In the event of a blind break, the Medical Monitor(s) will be notified through the electronic data capture system. The patient for whom the blind is broken should be subsequently withdrawn from the study. The details regarding the process of breaking the blind are outlined in the Medical Monitoring Plan and the Pharmacy Manual.

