12.4.2. Efficacy

The primary analysis targets an effect of treatment (response rates at 24 weeks) among subjects given the opportunity for treatment who are dispensed study drug. The treatment policy strategy is used for the intercurrent event of discontinuation of study treatment (either temporarily or permanently) and so the response rates at 24 weeks are of interest, irrespective of continued therapy, in line with the intent-to-treat principle.

For the primary efficacy analysis and the key secondary efficacy analysis, a 0.025 (two-sided) alpha-level will be allocated to each dose for comparison with placebo to adjust for multiplicity of testing associated with two doses. Additional secondary endpoints will be tested in the following order (see Section 12.4.3) and be considered statistically significant and alpha-level protected if they (and all prior endpoints in the hierarchy for that dose versus placebo) achieve statistical significance at the 0.025 level of significance. Irrespective, nominal p-values will be provided. Testing will be performed only for the Treatment Period. Missing values will be handled as specified in Section [12.4.4](#).

Primary Efficacy Endpoint

The primary efficacy endpoint will be the proportion of patients achieving an absolute SALT score ≤ 20 at Week 24. Pairwise treatment group differences from placebo will be assessed with the Cochran-Mantel-Haenszel test using baseline scalp hair loss (partial vs complete/near-complete) as the stratification factor, for each active treatment group versus placebo.

Other Efficacy Endpoints

[figure not shown]
For proportions of patients achieving specified improvement criteria (eg, CGI-I and PGI-I responders), pairwise treatment group differences from placebo at each scheduled evaluation will be assessed with the Cochran-Mantel-Haenszel test using baseline scalp hair loss as the stratification factor.

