8.2.3. Sensitivity Analyses of the Primary Analysis

Sensitivity analyses of the primary efficacy endpoint will be conducted to evaluate the robustness of study results under different assumptions and imputation algorithms. For the primary endpoint, categorized as absolute SALT score ≤ 20 at Week 24, the following sensitivity analyses will be performed for the Efficacy Population only.

Sensitivity 1: Multiple imputation; missing not at random (MNAR)

This sensitivity analysis is an implementation of a pattern mixture model that draws from different populations based on the reason for withdrawal from study. Patients who discontinued the study early due to a treatment-emergent adverse event (including COVID-19) or due to lack of efficacy will be considered MNAR. Treatment-emergent adverse event and lack of efficacy are reasons collected under “If 'Withdrew Consent', specify reason” on the *Study Discontinuation/Completion eCRF* page.

For patients who discontinued the study early due to a treatment-emergent adverse event or lack of efficacy, SALT scores missing after discontinuation will be imputed using the control arm. This assumes that patients, regardless of treatment, who discontinue the study early for those reasons would have similar SALT scores to placebo patients with complete data.

For patients who discontinued the study due to reasons other than treatment-emergent adverse event or lack of efficacy, missing SALT scores after subjects discontinue the study early will be multiply imputed from subjects within the same treatment group who have complete data at that time. Terms will include baseline values and the weekly data through the time point being imputed.

The proportion of patients who have a SALT score ≤ 20 will be calculated for each imputed dataset. The primary analysis, as described in Section 8.2.2, will be repeated for the Efficacy Population using the MI with MNAR assumption datasets.

Sensitivity 2: Tipping point

Additionally, a tipping point sensitivity analysis will be conducted for each dose compared to placebo at Week 24 if the result of the MI analysis is statistically significant at the alpha ≤ 0.025 level, in favor of treatment, for the given dose. The tipping point analysis will use the primary MAR assumption datasets, where all imputed values are adjusted.

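### Protocol 8.4 withdraws unblinded patients from the study, against the follow-up rule in 8.3 and the treatment-policy aim in 12.4.2, creating a small amount of avoidable, adverse-event-related missing Week 24 data

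*Protocol*

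**What the plan says.** **Blind break.** Protocol 8.4 gives one trigger: "In the case of a medical requirement to break the blind to determine appropriate treatment for an adverse event". Its consequence is: "The patient for whom the blind is broken should be subsequently withdrawn from the study".

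**Follow-up after stopping drug.** Protocol 8.3 states as its intent that "patients who discontinue study medication (at any time) for any reason will continue to be followed for all protocol-planned study visits", through the end of the 24-week period and with efficacy endpoints collected. The study withdrawal it makes mandatory is for consent: "The Investigator must withdraw any patient from the study if the patient withdraws consent and requests to stop participating in the study". Section 7.1 and the synopsis likewise keep patients who stop for intolerable symptoms in the study unless they withdraw consent.

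**Estimand.** Protocol 12.4.2: "The treatment policy strategy is used for the intercurrent event of discontinuation of study treatment". Week 24 response is of interest irrespective of continued therapy.

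**Missing data.** SAP 8.2.1 imputes missing SALT under MAR, separately by arm, from baseline SALT and the patient's own earlier observed or imputed scores. In SAP 8.2.3, Sensitivity 1 imputes from the control arm after study discontinuation for a treatment-emergent adverse event or lack of efficacy. On the source of those reasons it says: "Treatment-emergent adverse event and lack of efficacy are reasons collected under" the follow-up question to withdrawn consent on the study discontinuation page. Sensitivity 2, the tipping point analysis, shifts all imputed values, for a dose whose imputed-data result is significant at 0.025.

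**The concern.** The two sections give a site incompatible instructions for the same patient. Someone withdrawn from the study under 8.4 is necessarily off study drug as well, and 8.3 says that a patient off drug for any reason is still followed. Sites may resolve the conflict differently.

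A site that follows 8.4 ends SALT and SPRO collection for a reason tied to an adverse event, where the assumption that the patient resembles others in the same arm is hard to defend. If such patients regrow less hair off drug than their arm-mates, imputing from the arm favours the active dose. Patients are not replaced, so the Week 24 outcome of a randomised patient is lost for good. The summary of changes for Amendment 2 gives the separation of treatment withdrawal from study withdrawal as the reason for edits to the synopsis and to 7.1, 8.3 and 9.2. It does not name 8.4 for that change, so 8.4 may simply have been left behind; that is inference.

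**Working it through.** **1. What happens to the data under 8.4.**
- Week 24 SALT is missing unless an early termination visit falls on Day 166 to 172, the Week 24 efficacy window in SAP 8.1.2.
- The primary analysis imputes it within arm under MAR (SAP 8.2.1). SPRO is imputed on the same principle by logistic regression (SAP 8.3.1).
- Sensitivity 1 takes the adverse-event reason from the withdrawn-consent item. A patient removed under 8.4 need not have withdrawn consent. Neither document says how that withdrawal is coded, and Protocol 8.3.1 on recording reasons is written only for withdrawn consent. The patient may therefore be imputed from the same arm again.
- Sensitivity 2 includes the patient however the withdrawal is coded. At its maximum, a treated patient's imputed improvement is set back to baseline, which is non-response.
- SAP 8.2.3 specifies these sensitivity analyses for the primary endpoint only, so SPRO has none.

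**2. The plan's own power figures.** Inputs from Protocol 12.1: response 40%, 25% and 10%; n = 210, 350 and 140; two-sided alpha 0.025 (z = 2.241).

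Power = Φ([p − p₀ − z·√(p̄(1 − p̄)(1/n + 1/n₀))] / √(p(1 − p)/n + p₀(1 − p₀)/n₀)).

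For 8 mg, p̄ = (87.5 + 14)/490 = 0.207, so power = Φ((0.15 − 2.241 × 0.0405)/0.0343) = 95.8%. An exact calculation with continuity correction gives 94.7%, close to the stated 94%. For 12 mg, power exceeds 99.9% (stated: above 99%). The conflict does not depend on these figures; they are the baseline for step 4.

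**3. Size of the overstatement.** Let u be the fraction of an active arm unblinded and withdrawn, p the arm's planned response rate, and q the rate these patients would truly show at Week 24. If imputation reproduces the arm rate, overstatement = u(p − q). The documents give neither u nor q; both are assumed.

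| Arm | u | Patients | q = 10% | q = 0% |
|---|---|---|---|---|
| 12 mg, p = 40% | 0.5% | 1.05 | 0.15 points | 0.20 points |
| 12 mg | 2% | 4.2 | 0.6 | 0.8 |
| 12 mg | 5% | 10.5 | 1.5 | 2.0 |
| 8 mg, p = 25% | 0.5% | 1.75 | 0.075 | 0.125 |
| 8 mg | 2% | 7 | 0.3 | 0.5 |
| 8 mg | 5% | 17.5 | 0.75 | 1.25 |

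Example: 0.02 × (0.40 − 0.10) = 0.006, or 0.6 points. With q = 10%, the placebo arm's own overstatement is u(0.10 − 0.10) = 0, so the active-arm figure is also the overstatement of the difference.

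**4. Effect on power if these patients are counted at q.** For 8 mg, power moves from 95.8% to 94.5–95.0% at u = 2% and to 92.1–93.8% at u = 5%. For 12 mg it stays above 99.9%.

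**The case against.** The best defence is that the numbers are few and the plan already guards against them. The tipping point analysis moves every imputed value, as far as non-response for treated patients, and it runs whenever a dose is significant, which is when an overstatement would matter to the claim. That stands for the primary endpoint. It tests the missing data but does not recover them, and it does not reach SPRO.

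Three narrower objections also have force. Section 12.4.2 applies treatment policy to stopping treatment and does not name unblinding, so 8.4 conflicts with the aim of the estimand rather than with a stated rule for unblinded patients. Section 8.3 does not say that withdrawn consent is the only route out, since it also provides: "Patients who withdraw or are withdrawn from the study will not be replaced". And SALT is a live site rating, so scores after unblinding may come from a rater who knows the arm. That is a real cost of keeping them.

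A reader might infer more than the documents support:
- *That safety follow-up is lost altogether.* Section 11.3 follows adverse events until they stabilise or are explained, and the schedule of assessments has an early termination visit and a Week 28 safety visit. What is lost is the remaining scheduled visits, with their routine laboratory tests and efficacy assessments.
- *That the rule removes the patients with the worst adverse events.* The trigger is needing the assignment to choose treatment, not a severity grade. A severe event handled without unblinding stays under 8.3.
- *That each such patient is imputed at the arm's average rate.* The model uses the patient's own earlier SALT scores.
- *That Sensitivity 1 certainly misses them.* That depends on an eCRF page not in these documents. Its substantive rule is discontinuation due to an adverse event, so misclassification is possible, not shown.

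**Conclusion.** The conflict is real and lies in current text. Section 8.4 cannot be followed together with 8.3, 7.1 and the synopsis, and it works against the aim in 12.4.2. Following it creates avoidable missing outcomes related to adverse events.

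The effect is small. With 0.5% to 2% unblinded, response is overstated by about 0.15 to 0.6 points for 12 mg and 0.075 to 0.3 points for 8 mg if these patients respond at 10%, and by up to 0.8 and 0.5 points if none respond. The planned differences from placebo are 30 and 15 points. These are approximate upper-range figures, not bounds: they use the arm rate, whereas imputation conditions on each patient's history. They rest on an assumed unblinding rate and on the assumption that unblinded patients do worse than their arm-mates. On these assumptions the primary conclusion would not change. This is a defect of consistency and estimand, worth correcting because the correction is cheap.

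**What to change.** **Protocol.** Reconcile 8.4 with 8.3 and 12.4.2 so that a blind break alone does not end outcome data collection; SALT and SPRO would continue through Week 24 unless consent is withdrawn. What a blind break means for study drug and other clinical management is for the sponsor to settle and state consistently. Record the unblinding date in the eCRF. Section 9.5, which ties prohibited medication to withdrawal from the study, sits uneasily with 8.3 in the same way and can be reconciled in the same amendment.

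**SAP.**
- Use observed post-unblinding SALT in the primary analysis.
- Add one sensitivity run that counts unblinded patients as non-responders.
- Define the adverse-event category of Sensitivity 1 so that it includes study withdrawals that follow an adverse event without withdrawn consent.

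**Cost.** A short protocol change, one data field, one clarified definition and one extra run. The downside is a few ratings by a possibly unblinded rater, which the non-responder run addresses.

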8.5. Criteria for Study Termination

The DMC will review cumulative safety data at regular intervals throughout the study. Should safety signals arise that suggest treatment with CTP-543 poses an unjustified risk to patients, termination of the study or modification of dosing arms may occur upon Sponsor review of the DMC recommendation. The DMC may call for unscheduled data review meetings at any time to ensure appropriate safety monitoring.

Events that could trigger an unscheduled review may include, but are not limited to:

High frequency of dose interruptions

High frequency of, or a trend in, SAEs

High frequency of Grade 3/4 adverse events

Trend in organ system-specific moderate and/or severe adverse events

High frequency of patient discontinuation of treatment due to adverse events

The Sponsor will notify Investigators of any recommendation of study termination by the DMC. The Sponsor will notify Investigators of recommendation for study modification as necessary to protect patient safety including appropriate instructions for removing patients from treatment, while maintaining the blind.

Any termination required by the Sponsor must be implemented by the Investigator, if instructed to do so, in a time frame that is compatible with the patient's well-being. The Sponsor reserves the right to discontinue the study at any time for clinical or administrative reasons.

9. DESCRIPTION OF STUDY TREATMENTS

9.1. Description of Treatments

Patients will be stratified by extent of scalp hair loss and randomized to CTP-543 or placebo in a 3:5:2 ratio (12mg BID:8 mg BID: placebo).

Treatments arms will include:

- 12 mg CTP-543 every 12 hours
- 8 mg CTP-543 every 12 hours
- Placebo every 12 hours

For each treatment arm, patients will take the first dose of study drug in the clinic on Day 1 of the Treatment Period and will be instructed to take study drug approximately every 12 hours (\pm 3 hours) without regard to food for the duration of the study.

9.2. Dose-Adjustment Criteria

No individualized dose adjustment is allowed during the Treatment Period except in the event of intolerability, for which a dose interruption or patient discontinuation may occur at the judgement of the Investigator in consultation with the Medical Monitor (see Section 9.2.1 below for details).

The DMC will review cumulative safety data throughout the study in accordance with the DMC Charter. If the DMC determines that the high dose of CTP-543 should be stopped for safety reasons, patients receiving treatment at that dose will move to the low dose of CTP-543 at the patient's next visit. If an immediate hazard is suspected, patients without an imminent visit may have an **Unscheduled Visit** for potential dose adjustment to maintain the blind. In the event of CTP-543 treatment arm cessation and dose adjustment to the low dose of CTP-543 treatment, the blind will be maintained and individual patient treatment modifications will not be disclosed.

9.2.1. Dose Interruption Safety Criteria and Management

Patients who experience hematologic adverse events as described in [Table 3](#), significant clinical laboratory abnormality, or adverse events that may reflect an unfavorable risk-benefit profile may have their dose interrupted at the discretion of the Investigator. The Medical Monitor(s) should be consulted whenever possible prior to decisions for dose interruption.

Patients who withdraw consent and therefore are discontinued from the study should undergo an **Early Termination Visit** and associated adverse events should be followed as described in [Section 11](#) Adverse Events.

Hematology parameters will be assessed bi-weekly for the first 4 weeks of the Treatment Period, and every 4 weeks thereafter for the remainder of the study. Prior to dose interruption, hematology parameters should be confirmed with repeat testing at an **Unscheduled Visit** within 72 hours, except in severe cases (i.e.: neutrophil counts below $0.5 \times 10^9/L$) where immediate interruption of dosing is necessary for the safety of the patient. **Blood draws confirming dose interruption criteria should occur prior to the first daily dose on the day of draw.**

Dose interruption requirements for hematologic abnormalities are provided below. However, less significant changes may warrant clinical intervention and the Investigator should use his/her best clinical judgment when considering a dose interruption whether for singular or aggregate hematology results above the limits provided in Table 3, or for other clinical signs, symptoms, or considerations that suggest dose interruption is in the best interest of the patient.

Table 3: Selected Hematologic Thresholds for Dose Interruption

Neutrophil Count	Dose Adjustment
Between 0.5 to 1 x 10 ⁹ /L (Grade 3)	Interrupt dose until recovered to greater than 1.5 x 10 ⁹ /L and resume dosing at previous dose
Less than 0.5 x 10 ⁹ /L (Grade 4)	Severe case: Interrupt dose immediately and repeat CBC with differential within 72 hours. Recommend hematology consult and contact medical monitor. Permanent discontinuation of treatment should occur upon repeat confirmation of value
Female Hemoglobin Level	Dose Adjustment
Less than 10 g/dL	Interrupt dose until recovered to greater than 10.5 g/dL and resume dosing at previous dose
Male Hemoglobin Level	Dose Adjustment
Less than 11.5 g/dL	Interrupt dose until recovered to greater than 12 g/dL and resume dosing at previous dose
Platelet Count	Dose Adjustment
Less than 75 x 10 ⁹ /L	Interrupt dose until recovered to greater than 100 x 10 ⁹ /L and resume dosing at previous dose
Greater than 750 x 10 ⁹ /L	Interrupt dose until recovered to less than 600 x 10 ⁹ /L and resume dosing as prescribed by the Investigator

Upon dose interruption, the parameters that triggered the interruption should be monitored at least weekly until either: 1) recovery above the threshold for dosing resumption is achieved, or 2) a 21-day dose interruption period has elapsed, at which time a discussion between the PI and the Medical Monitor should occur to evaluate whether or not the subject should discontinue treatment permanently. In the case of severe neutropenia (neutrophil counts less than 0.5 x 10⁹/L) patient should interrupt dose **immediately** and repeat CBC with differential within 72 hours. The Medical Monitor should be contacted and a hematology consult should be made if appropriate. Permanent discontinuation of treatment should occur upon repeat confirmation of value. Patients who discontinue treatment due to lack of acceptable recovery of parameters should continue to be followed for all safety and efficacy assessments through the completion of the 24-week treatment period, and will have all endpoints (including efficacy) collected accordingly.

Subjects with both a positive SARS-CoV-2 test (antigen or antibody) AND signs or symptoms consistent with SARS-CoV-2 infection should immediately interrupt dosing with study drug. Dose interruption should continue until symptoms subside (it is not necessary to have a negative SARS-CoV-2 test result). If symptoms do not subside within a 21-day dose interruption period, a discussion between the PI and the Medical Monitor should occur to evaluate whether or not the

subject should discontinue treatment permanently. Signs and symptoms include, but are not limited to: fever or chills, cough, shortness of breath or difficulty breathing, fatigue, muscle or body aches, headache, new loss of taste or smell, sore throat, congestion or runny nose, nausea or vomiting, diarrhea, trouble breathing, persistent pain or pressure in the chest, new confusion, inability to wake or stay awake, bluish lips or face.

Subjects who have signs or symptoms consistent with SARS-CoV-2 infection should be tested for SARS-CoV-2 and do not have to dose interrupt unless the test result is positive. Subjects who have a positive SARS-CoV-2 test (antigen or antibody) but do not have any signs or symptoms consistent with SARS-CoV-2 infection are not required to dose interrupt.

Table 4: SARS-CoV-2 Dose Interruption Criteria

SARS-CoV-2 Test Result	SARS-CoV-2 Symptoms	Dose Interruption
Positive	Yes	Yes
Positive	No	No
Negative	Yes	No

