be assessed every 4 weeks throughout the Treatment Period. In light of the COVID-19 pandemic, challenges in the conduct of study visits may arise from quarantines, site closures, and/or travel limitations. To ensure the safety of trial participants and to minimize risk to trial integrity, alternative methods for drug dispensation and assessments, including telemedicine visits and clinical laboratory blood draws at a local laboratory or via a Home Health Care agency, may be offered for those trial participants who may no longer have access to the investigational site. Additional information will be documented in study manuals. Significant cytopenias or other hematologic abnormalities will be managed by severity through dose interruption or discontinuation, and signs and symptoms of infection will be closely monitored and treated promptly. Patients who experience intolerable symptoms during treatment may discontinue treatment at the judgement of the Investigator, but will continue in the study and complete all assessments unless they withdraw consent. Patients may withdraw consent at any time.

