9. History of a lymphoproliferative disease or malignancy, other than non-melanoma skin cancer or cervical carcinoma. Patients with 3 or more basal or squamous cell carcinomas diagnosed in the past 2 years are excluded.
10. History of solid organ or hematological transplantation.
11. Fever, inflammation, or systemic signs of illness suggestive of systemic or invasive infection or a positive SARS-CoV-2 test result within 2 weeks prior to Baseline.
12. Abnormal levels of thyroid stimulating hormone at Screening, defined as <0.9 x the lower limit of normal (LLN) and >1.5 x the upper limit of normal (ULN).

13. Screening labs outside the normal range for parameters associated with potential risk for treatment under investigation. This will include but is not limited to:
 - a) Platelets $\leq 100 \times 10^9/L$ or $\geq 600 \times 10^9/L$
 - b) Absolute neutrophil count $\leq 1.5 \times 10^9/L$
 - c) Hemoglobin levels ≤ 10.5 g/dL for females, or hemoglobin levels ≤ 12.0 g/dL for males
14. Screening blood level of hemoglobin A1c $\geq 7.5\%$ (58 mmol/mol, 9.3 mmol/L).
15. Abnormal liver function at Screening, defined as $\geq 2 \times$ ULN of serum alanine transaminase, serum aspartate transaminase, and serum alkaline phosphatase, or $\geq 1.5 \times$ ULN total bilirubin (unless isolated Gilbert's syndrome).
16. Abnormal renal function (estimated glomerular filtration rate < 60 mL/min/1.73 m² using the CKD-EPI 2009 equation) at Screening.
17. Patient has positive results for hepatitis B surface antigens (HBsAg), antibodies to hepatitis B core antigens (anti-HBc), or hepatitis C virus (HCV) at Screening, or known history of human immunodeficiency virus infection. Subjects who test positive for HCV but who are in remission (sustained virologic response as evidenced by undetectable HCV RNA level using a sensitive assay ≥ 12 weeks after completion of HCV therapy) are allowed inclusion in the study.
18. Vaccination with a live attenuated vaccine during the study or up to 6 weeks prior to randomization.
19. History of previous active disease due to *M. tuberculosis* (TB) without documentation of successful treatment; OR, patient has a positive result from a Tuberculin Skin Test (TST) or a QuantiFERON-TB Gold (QFT) test performed at Screening.

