Third, treatment-emergent potentially clinically significant (PCS) laboratory values will be identified. PCS values are defined as those that meet Grade 3 or Grade 4 toxicity criteria from the Common Terminology Criteria for Adverse Events (CTCAE) criteria. Laboratory values will be graded using CTCAE version 5.0, for those values included. CTCAE grades will be based solely on numeric results and without regard to other symptoms based on clinical judgment. For laboratory parameters whose CTCAE grading is independent of baseline criteria, treatment-emergent PCS laboratory values are those in which the baseline value is not PCS and the post-baseline value is PCS. For laboratory parameters whose CTCAE grading is dependent upon baseline criteria, any post-baseline grading of Grade 3 or Grade 4 will be considered treatment-emergent. The number and percentage of patients with treatment-emergent PCS laboratory values will be summarized by treatment group for each clinical laboratory variable.

These analyses will be repeated for serum chemistry results, hematology results, and lipid results (where lipid tests include total cholesterol, low-density lipoprotein, high-density lipoprotein,

triglycerides). Laboratory results will also be listed. Reference ranges for each clinical laboratory parameter will also be summarized in a data listing.

Box plots of hemoglobin, platelets, and neutrophils will also be provided with dose interruption limits included as reference lines (see Protocol Section 9.2.1).

Pregnancy test results will be listed only.

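### Protocol 9.2.1 makes dose interruption at the Table 3 haematologic thresholds both discretionary and required; the discretionary opening sentence is the part to correct

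*Protocol*

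**What the plan says.** The first sentence of Protocol 9.2.1 covers three groups of patients: those with the haematologic events listed in Table 3, those with another significant laboratory abnormality, and those with adverse events that suggest an unfavourable balance of risk and benefit. All three groups "may have their dose interrupted at the discretion of the Investigator".

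The lead-in to Table 3 uses different language: "Dose interruption requirements for hematologic abnormalities are provided below". The sentence after it reserves judgment for milder findings: "less significant changes may warrant clinical intervention and the Investigator should use his/her best clinical judgment when considering a dose interruption". The table rows are imperative. For female haemoglobin below 10 g/dL, for example, the row reads "Interrupt dose until recovered to greater than 10.5 g/dL and resume dosing at previous dose".

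The section asks for a repeat test within 72 hours before interrupting. It excepts neutrophils below 0.5 x 10^9/L, where "immediate interruption of dosing is necessary for the safety of the patient".

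Two other places bear on intent. Protocol 7.1 says "Significant cytopenias or other hematologic abnormalities will be managed by severity through dose interruption or discontinuation", and the Synopsis says the same. SAP 9.5 says "Box plots of hemoglobin, platelets, and neutrophils will also be provided with dose interruption limits included as reference lines".

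**The concern.** A threshold for stopping study drug is useful only if every site applies it in the same way. As written, two investigators with the same confirmed haemoglobin, platelet or Grade 3 neutrophil result could act in opposite ways, one interrupting and one continuing, and each could cite 9.2.1. About 70 sites are planned.

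The parameters are not incidental. Haemoglobin, neutrophils and platelets are the three listed under exclusion criterion 13 in Protocol 8.2, which is introduced as "Screening labs outside the normal range for parameters associated with potential risk for treatment under investigation". The stake is that a patient stays on drug past a limit that the protocol regards as a reason to pause.

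**Working it through.** No power, alpha or sample-size figure is involved. The check is a row count and a comparison of texts.

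**Step 1: count the rows and see which are settled elsewhere.** Cell counts are x 10^9/L.

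| Table 3 row | Table instruction | Opening sentence of 9.2.1 | Separate text that settles it? |
|---|---|---|---|
| Neutrophils 0.5 to 1 | Interrupt; resume above 1.5 | Discretionary | No |
| Neutrophils < 0.5 | Interrupt at once; stop for good if confirmed | Discretionary | Yes, interruption stated to be necessary |
| Haemoglobin, female, < 10 g/dL | Interrupt; resume above 10.5 | Discretionary | No |
| Haemoglobin, male, < 11.5 g/dL | Interrupt; resume above 12 | Discretionary | No |
| Platelets < 75 | Interrupt; resume above 100 | Discretionary | No |
| Platelets > 750 | Interrupt; once below 600, the manner of restarting is left to the Investigator | Discretionary | No |

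Total rows = 6. Rows made mandatory by other text in 9.2.1 = 1. Rows where the conflict is live = 6 - 1 = 5. In the last row, the Investigator's choice concerns only how dosing restarts, so that row still requires the interruption.

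**Step 2: can the discretion be confined to the other two groups?** No. The discretionary sentence refers to Table 3 by number, so it cannot be read as covering only other laboratory abnormalities and adverse events.

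**Step 3: is there a rule on which text prevails?** The protocol gives none for this section. Section 9.2 also uses discretionary language, but it sends the reader to 9.2.1 for the details and so does not settle the matter or add a second conflict.

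**Step 4: which reading was intended?** The mandatory one. The lead-in speaks of requirements, judgment is reserved for lesser changes, 7.1 and the Synopsis say that significant cytopenias will be managed by interruption or discontinuation, and the SAP treats the thresholds as limits. The SARS-CoV-2 rule in the same section also shows that an unambiguous form was available: Table 4 gives a plain yes or no for each combination of test result and symptoms.

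**Step 5: does it reach the primary analysis?** Not materially. Protocol 12.4.2 handles temporary and permanent discontinuation with a treatment policy strategy, and 8.3 intends that patients who stop drug are followed, with efficacy collected, through the 24-week treatment period.

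**The case against.** The best defence is that this is loose drafting and not a contradiction. The opening sentence is a general introduction to three categories, and the specific rule follows. On the ordinary principle that the specific governs the general, a site has one workable rule, and to keep dosing it would have to ignore both the lead-in and the row. There are also safeguards: central laboratory processing, repeat testing within 72 hours, consultation with the Medical Monitor where possible, and a DMC that may convene if interruptions are frequent.

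Much of this stands as evidence of intent, and it makes wide divergence less likely. It does not remove the conflict, because the general sentence itself cites Table 3 and nothing says that it yields. Medical Monitor consultation is not guaranteed and supplies no rule. If the mandatory reading is what was meant, that is a reason to correct the sentence.

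A reader might infer more than the documents support:

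- **That 8.3 contradicts Table 3 on confirmed neutrophils below 0.5 x 10^9/L.** Section 8.3 sends Grade 4 laboratory abnormalities to case-by-case review without naming an exception. But the same bullet lists bone marrow events among the reasons for mandatory discontinuation, and its examples for review are exercise-related CK rises, laboratory errors and artefacts, which a confirmed neutrophil count does not resemble. Section 9.2.1 states the specific outcome, permanent discontinuation. This is a minor ambiguity that the text largely settles.
- **That the narrow gap between entry limits and thresholds shows the size of the problem.** For haemoglobin the gap is 0.5 g/dL in both sexes (10.5 - 10.0 and 12.0 - 11.5). It would be the same if the wording were clear, so it does not measure the conflict. The same is true of the number of scheduled blood draws.
- **That exposure summaries or the Per Protocol analysis are compromised.** SAP 9.2 classifies interruptions that occurred, whether or not they were mandatory. Per Protocol membership depends on a sponsor classification of major deviations before database lock, is fixed before unblinding, and feeds only a supportive analysis.

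**Conclusion.** The point holds as an internal inconsistency in a safety rule. The opening sentence of 9.2.1 is wrong as written for 5 of the 6 Table 3 rows, and the mandatory reading is the evident intent. It should be corrected on grounds of patient safety and consistent handling across sites.

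The conclusion rests on the text alone. Without event frequencies, neither the number of patients who would reach a threshold nor the share of investigators who would use the discretion can be estimated. The documents do not support a claim that the primary efficacy result is at risk.

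**What to change.** In Protocol 9.2.1, remove the reference to Table 3 from the discretionary sentence. State that dosing must be interrupted at the Table 3 thresholds once they are confirmed by repeat testing, and immediately, before confirmation, for neutrophils below 0.5 x 10^9/L. Keep Investigator discretion for other significant laboratory abnormalities, for adverse events and for less marked haematologic changes.

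As an optional tidy-up in the same amendment, add a cross-reference in 8.3 to the Table 3 row for confirmed neutrophils below 0.5 x 10^9/L, so that it is not read as falling under the case-by-case Grade 4 laboratory clause. Limit the cross-reference to that row, so that the rows that allow dosing to resume are not drawn into mandatory discontinuation. Leave the 21-day rule as a case-by-case discussion with the Medical Monitor.

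The wording change is short, but a site clarification alone would not be enough. Protocol 13.4 requires an amendment for any permanent change, and because this one bears on patient safety it would not qualify as administrative, so sites would wait for IRB/EC approval. Endpoints, sample size and analysis are unchanged.
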